# 14.2 Statistical Design/Endpoints

## **Primary Endpoint**

The primary endpoint of this study is the proportion of patients who achieve a CR or a CRi (defined in section 13.1) compared to the historical rate of 0.45. It is hypothesized that the CR+CRi rate for alisertib in combination 7+3 induction chemotherapy will be 0.70. A one-sided single proportion test will be used to test the hypothesis that the remission rate of alisertib in 7+3 chemotherapy is greater than the 7+3 historical rate.

# **Secondary Endpoints**

The one year overall survival and relapse free survival after treatment will be estimated using the Kaplan-Meier method, and presented as a 90% confidence interval using Greenwood's formula for standard errors of the estimate. Overall survival (OS) is defined as the time from study entry to death from any cause. Relapse free survival (RFS) is defined as the time from achieving a CR to the first of disease recurrence or death. RFS applies only to the subset of patients who achieve a CR+CRi at the end of induction therapy. Remission duration will also be estimated using the method of Kaplan-Meier. All toxicities encountered during the study will be evaluated according to the NCI criteria assigned to the protocol (CTCAE version 4.0).

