## 1.3 Secondary Objectives

- To determine if the 1-year overall survival (OS) rate, relapse free survival (RFS), remission duration of higher risk patients receiving alisertib in combination with chemotherapy, and to assess whether this is higher than the historical rates seen in this population with conventional intensive chemotherapy alone.
- To describe the frequency and severity of adverse events for patients treated on this study.
- To describe the interaction of pretreatment disease and patient characteristics including morphology, cytogenetics, immunophenotype, molecular/genetic features, WBC count and hemogram, and performance status on clinical outcomes.
- To describe the pharmacodynamic effects of alisertib during treatment with this induction combination

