At our institution, we have just finished accrual on a phase I, 3+3 cohort dose-escalation study of alisertib combined with standard 7+3 induction for newly diagnosed AML. We recently presented our data at the oral session during the 2014 American Society of Hematology Conference. For this study, those with acute promyelocytic leukemia or with AML and core-binding factor alterations were excluded. All patients received 7+3 induction (continuous infusion cytarabine 100mg/m^2 x 7 days and intravenous idarubicin 12mg/m^2 x 3 days), after which on day 8, alisertib was administered twice daily (BID) for 7 days. Dose escalation occurred via three cohorts (10mg BID, 20mg BID, 30mg BID). All underwent a mid-induction bone marrow biopsy, following course of alisertib, to assess for residual disease, which if present, was to be treated with 5+2 re-induction (cytarabine 100mg/m^2 x 5 days, idarubicin 12mg/m^2 x 2 days) without alisertib. Following induction, up to four cycles of consolidation were allowed, using cytarabine (3g/m^2 BID days 1,3,5 for those aged <60 and  $2g/m^2$  daily days 1-5 for those aged  $\ge60$ ) followed by alisertib, according to dose cohort, on days 6-12. After consolidation, alisertib maintenance was initiated, at cohort dose level, for days 1-7 of 21 day cycles, to be continued for 12 months or until disease progression. Those eligible for stem cell transplant (SCT), following induction and/or consolidation courses, were removed from study for this purpose.

Data on 16 patients were presented (n=3, 10mg BID; n=7, 20mg BID; n=6, 30mg BID). One patient (6%) had therapy-related AML and six (38%) had antecedent MDS or myeloproliferative neoplasm. Eleven of the 16 patients (69%) had high risk disease, as per older age (age over 65), high risk cytogenetics, and /or derived from preceding myeloid malignancy. *FLT3* mutations were detected in 3 (19%), *NPM1* mutations in 3 (19%), *CEBPA* mutations in 2 (13%), and *IDH1/IDH2* mutations in 6 patients (38%). One patient in cohort 2 died of sepsis, deemed unrelated to study drug, prior to completion of the toxicity assessment period and was replaced. Six (38%) patients have gone on to SCT. All patients received induction, and 9 patients received at least one cycle of consolidation, and 3 patients started maintenance therapy. Alisertib was well tolerated. All patients experienced expected grade 4 toxicities of anemia, thrombocytopenia, and febrile

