#### 13. MEASUREMENT OF EFFECT

## 13.1 Response Criteria

Complete remission (CR): Bone marrow showing less than 5% myeloblasts with normal maturation of all cell lines, an ANC of at least 1000/μL and a platelet count of 100,000/μL, absence of blast in peripheral blood, absence of identifiable leukemic cells in the bone marrow, existing extramedullary disease. If possible, at least one bone marrow biopsy should be performed to confirm CR.

Complete Remission with Incomplete Blood Count Recovery (CRi): Same as for CR but without achievement of ANC at least 1000/uL (CRi) and/or platelet count of 100,000/uL (CRp).

**Partial Remission:** All hematologic criteria of CR are fulfilled, and a decrease of bone marrow blast percentage to 5 to 25 percent; and decrease of pretreatment bone marrow blast percentage by at least 50 Percent.

**Morphologic Leukemia Free State:** Bone marrow blasts <5 percent; absence of blasts with Auer rods; absence of extramedullary disease; no hematologic recovery required

Resistant Disease: Failure to achieve CR or CRi.

**Recurrence/Morphologic Relapse**: Reappearance of leukemic blasts in the peripheral blood or > 5% blasts in the bone marrow not attributable to any other cause (e.g. bone marrow regeneration

after consolidation therapy). The appearance of new dysplastic changes should be considered

relapse. The reappearance or development of cytologically proven extramedullary disease indicates relapse. Molecular and/or genetic relapse is characterized by reappearance of a cytogenetic or molecular abnormality.

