#### 14. STATISTICAL CONSIDERATIONS

This is a phase II, two-stage, single center, to assess the efficacy of alisertib in combination 7+3 induction chemotherapy in the adult higher risk AML population. Higher risk AML patients are those that (a) are at least 18 years of age with a poor risk karyotype and/or secondary AML, or (b) at least 65 years of age with AML.

The primary endpoint of this study is the rate of complete remission (CR) or complete remission with incomplete count recovery (CRi) in higher risk patients receiving alisertib in combination with 7+3 induction chemotherapy. The CR+CRi rate will be compared to the historical rates seen in this population with 7+3 induction alone. Secondary endpoints include: 1-year overall survival (OS), relapse free survival (RFS), remission duration, and toxicity for patients receiving alisertib in combination with conventional cytotoxic chemotherapy.

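### Remission duration is given a Kaplan-Meier analysis but no definition; if it means time to relapse, the cumulative incidence of relapse should be reported, with death in remission as a competing event

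*Combined protocol and SAP*

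**What the plan says.** Section 14 names remission duration as an endpoint in its own right: "Secondary endpoints include: 1-year overall survival (OS), relapse free survival (RFS), remission duration, and toxicity". Section 1.3 groups it with 1-year OS and RFS and aims "to assess whether this is higher than the historical rates seen in this population with conventional intensive chemotherapy alone".

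Under Secondary Endpoints, section 14.2 defines OS by start and event. RFS gets a start, an event and a population: "Relapse free survival (RFS) is defined as the time from achieving a CR to the first of disease recurrence or death", and "RFS applies only to the subset of patients who achieve a CR+CRi at the end of induction therapy". OS and RFS estimates are to be "presented as a 90% confidence interval using Greenwood's formula for standard errors of the estimate". For remission duration there is one sentence: "Remission duration will also be estimated using the method of Kaplan-Meier". It gives no start, event, censoring rule or interval.

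Section 13.1 defines relapse by disease findings, beginning "Reappearance of leukemic blasts in the peripheral blood or > 5% blasts in the bone marrow not attributable to any other cause". Death is not among them. Section 5.2.5 lets patients come off study for transplantation, and no analysis rule covers this. Section 14 contains no competing-risk method.

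**The concern.** RFS already takes the first of relapse or death. An endpoint listed beside it most naturally differs by counting relapse alone. Kaplan-Meier then handles a death in remission as censoring, as if that patient could still relapse later. Death in remission rules relapse out, so one minus the Kaplan-Meier estimate is not the proportion of patients who relapse. Nor does the curve show the proportion alive and still in remission; it lies above that.

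The setting makes such deaths plausible: patients aged 65 or over or with high-risk disease, intensive consolidation, and some transplantation. In the preceding phase I study of this combination, "Six (38%) patients have gone on to SCT" (section 2.1.4.2).

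At stake is how durability of remission is described and set against historical rates. With the definition left open, the event could also be chosen after the data are seen.

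**Working it through.** **The plan's own figures.** None is given for remission duration. The Simon design in 14.1 reproduces by exact binomial calculation: early stopping 0.6437 under 0.45 (stated 0.64), type I error 0.0468 (limit 0.05), power 0.9054 under 0.70 (stated 0.90). Nothing below changes these.

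**The two readings side by side.**

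- *Death in remission is an event.* Kaplan-Meier is valid. The events are those of RFS, so the endpoint adds little.
- *Only relapse is an event.* A standard Kaplan-Meier analysis censors deaths in remission. The size of the resulting error depends on how many such deaths there are.

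**Size under the second reading.** The documents give no 1-year relapse or non-relapse death rates, so both are assumed, with constant cause-specific hazards over one year. Let R be the true 1-year proportion relapsing and D the true proportion dying in remission.

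- Total cumulative hazard: L = -ln(1 - R - D)
- Relapse part: Lr = L x R/(R + D)
- One minus Kaplan-Meier with deaths censored: 1 - exp(-Lr)
- Overstatement of relapse: 1 - exp(-Lr) - R

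Example, R = 0.40 and D = 0.10: L = -ln(0.50) = 0.6931; Lr = 0.6931 x 0.8 = 0.5545; 1 - exp(-0.5545) = 0.426; overstatement 2.6 points.

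| R | D | 1 - KM | Overstatement of relapse (points) | KM curve | True alive in remission (1 - R - D) |
|---|---|---|---|---|---|
| 0.40 | 0 | 0.400 | 0 | 0.600 | 0.60 |
| 0.40 | 0.05 | 0.412 | 1.2 | 0.588 | 0.55 |
| 0.40 | 0.10 | 0.426 | 2.6 | 0.574 | 0.50 |
| 0.40 | 0.20 | 0.457 | 5.7 | 0.543 | 0.40 |
| 0.50 | 0 | 0.500 | 0 | 0.500 | 0.50 |
| 0.50 | 0.05 | 0.516 | 1.6 | 0.484 | 0.45 |
| 0.50 | 0.10 | 0.534 | 3.4 | 0.466 | 0.40 |
| 0.50 | 0.20 | 0.577 | 7.7 | 0.423 | 0.30 |

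The last two columns show the opposite misreading. Taken as the proportion still in remission, the same curve is too high by 3.4 to 14.3 points when D is 0.05 to 0.20.

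**Another parameterisation.** Fix one minus Kaplan-Meier at 30-50% and the net 1-year probability of death in remission at 5-30%. With Lr and Ld the corresponding cumulative hazards, the cumulative incidence is Lr/(Lr + Ld) x (1 - exp(-(Lr + Ld))). The overstatement is then 0.7 to 7.1 points.

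**Against sampling error.** At a response rate of 0.70, 39 x 0.70 = 27.3 responders are expected. With 27 and no censoring, the 90% half-width is 1.645 x sqrt(0.5 x 0.5/27) = 15.8 points at an estimate of 0.5, and 1.645 x sqrt(0.7 x 0.3/27) = 14.5 points at 0.7.

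**The case against.** A reader might infer that the plan censors deaths in remission. No sentence says so. Separate listing suggests it without proving it: remission duration could instead differ from RFS in its start, in its population (14.2 dates RFS from CR but applies it to CR and CRi patients), or in how transplantation is treated. A reader might also infer that Kaplan-Meier is wrong however the endpoint is defined. It is not. If death is an event the estimate is valid, and overlap with RFS is redundancy, not error. Even with deaths censored, the curve is a legitimate cause-specific summary; the error lies in reading a relapse probability from it, which 14.2 does not propose.

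The size is also open to challenge. Section 2.1.4.2 reports that 7 of 19 phase I remitters (37%) relapsed and 5 of those died of relapsed AML. It mentions no death in remission among them, which points weakly to the low end of the range, although follow-up is not stated. The illustrated relapse bias is smaller than the confidence half-width, and overstating relapse would not flatter alisertib. No historical remission-duration figure or test is specified.

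All of this stands, and it keeps the point conditional and modest. It does not remove it. The endpoint still needs a definition, the most natural one does not suit the stated method if relapse probabilities are wanted, and the bias is systematic: the interval does not show it and more patients would not remove it. Read as the proportion still in remission, the curve errs in the favourable direction.

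**Conclusion.** The point holds conditionally. Remission duration is undefined as to start, event, death in remission and transplantation. On the natural relapse-only reading, the planned Kaplan-Meier analysis would overstate the probability of relapse by about 1 to 8 percentage points at one year. That range rests on assumed constant hazards, 40-50% relapse and 5-20% death in remission, none of which comes from the documents; with no deaths in remission the overstatement is zero. If death is an event, there is no bias but little is gained over RFS. Kaplan-Meier is appropriate for OS and RFS. The endpoint is descriptive and unsized, and the primary decision rule is untouched. The change is worth making because it is cheap and settles the definition before analysis.

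**What to change.** In section 14.2, replace the sentence on remission duration with wording to this effect: remission duration is the time from first CR or CRi to relapse as defined in 13.1; it will be summarised by the cumulative incidence of relapse, with death in remission as a competing event (Aalen-Johansen estimate, 90% confidence interval).

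Add that patients who leave study for transplantation continue to be followed for relapse and death, and state how transplantation is handled in the analysis. Keep Kaplan-Meier for OS and RFS. Label any Kaplan-Meier curve of remission duration as cause-specific, and do not read relapse probabilities from it.

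The cost is a few sentences and one standard analysis routine. Section 5.5 already provides for disease and survival status at least every 3 months for up to 12 months, so no new data item is needed; the team should confirm that this contact covers patients who have left for transplantation. Sample size and stopping rule stay as they are.

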## 15. PUBLICATION PLAN

[name] holds the primary responsibility for publications related to this study. The results should be made public within 24 months of reaching the end of the study. The end of the study is the time point at which the last data items are to be reported, or after the outcome data are sufficiently mature for analysis, as defined in the section on Sample Size, Accrual Rate and Study Duration. If a report is planned to be published in a peer-reviewed journal, then that initial release may be an abstract that meets the requirements of the International Committee of Medical Journal Editors. A full report of the outcomes should be made public no later than three (3) years after the end of the study.

# APPENDIX A PERFORMANCE STATUS CRITERIA

ECO	OG Performance Status Scale	Karnofsky Performance Scale		
Grade	Descriptions	Percent	Description	
0	Normal activity. Fully active, able		Normal, no complaints, no evidence of disease.	
U	to carry on all pre-disease performance without restriction.	90	Able to carry on normal activity; minor signs or symptoms of disease.	
1	Symptoms, but ambulatory. Restricted in physically strenuous activity, but ambulatory and able to carry out work of a light or sedentary nature ( e.g. , light housework, office work).		Normal activity with effort; some signs or symptoms of disease.	
1			Cares for self, unable to carry on normal activity or to do active work.	
2	In bed <50% of the time. Ambulatory and capable of all self-care, but unable to carry out	60	Requires occasional assistance, but is able to care for most of his/her needs.	
	any work activities. Up and about more than 50% of waking hours.		Requires considerable assistance and frequent medical care.	
3	In bed >50% of the time. Capable of only limited self-care, confined		Disabled, requires special care and assistance.	
3	to bed or chair more than 50% of waking hours.	30	Severely disabled, hospitalization indicated. Death not imminent.	
	4 100% bedridden. Completely disabled. Cannot carry on any self-care. Totally confined to bed or chair.		Very sick, hospitalization indicated. Death not imminent.	
4			Moribund, fatal processes progressing rapidly.	
5	Dead.	0	Dead.	

# **ADDENDUM B**

Adverse Risk Karyotype Groups per European Leukemia Net (ELN) Guidelines Döhner H et al, Blood 2010;115(3):453-474

- Inv(3)(q21q26.2) or t(3;3)(q21;q26.2)
- t(6;9)(p23;q34)
- t(v;11)(v;q23), [not including t(9;11)(p22;q23)]\*
- Monosomy 5 or del(5q)
- Monosomy 7
- Abnormal 17p
- Complex karyotype (≥3 abnormalities)
